12.1.2. DLT validation committee

For the dose escalation part, the DLT validation committee will be consulted before the first escalation to a new dose level.

Members for the DLT validation committee are the following (all at Institut Bergonié):

- An investigator ,
- A statistician,
- A pharmacist.

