3.4.2. Dose levels

- Dose escalation study assessing 4 dose levels of Olaparib in association with concomitant radiotherapy.

Level	-1	1	2	3	4
Olaparib	25 mg (daily)	25 mg (b.i.d)	50 mg (b.i.d)	100 mg (b.i.d)	150 mg (b.i.d)

- The starting dose of Olaparib is 25 mg b.i.d.
- The maximum dose of Olaparib administered (150 mg x 2) will not be exceeded.
- No skipping of the dose will be allowed.
- For a given patient, dose will never be escalated.
- **As long as no DLT is observed**, patients will be allocated to 4 dose levels following a 3+3 design with the following characteristics:
 - Inclusions of cohorts of 3 patients,
 - At dose levels 1 and 2, before accrual to next higher dose level, at least 2 patients with 6-week follow-up will be required,
 - At dose level 3, before accrual to dose level 4, at least 2 patients with 8-week follow-up will be required

- **As soon as the first DLT is observed**, patients will be allocated following a TITE-CRM design [Normolle et al. Statistics in Medicine 2003]. When a patient is eligible for enrollment, the probability of DLT is estimated for each dose level, based on the trial experience up to that time and the prior expectations for toxicity.
 - Each new patient is assigned to the currently estimated target dose, defined as the dose having an estimated probability of toxicity closest to but not greater than the target rate (33%), subject to the following restrictions :
 - A minimum of 2 patients will be entered on each dose level,
 - At dose levels 1 and 2, before accrual to next higher dose level, at least 2 patients with 6-week follow-up will be required,
 - At dose level 3, before accrual to next higher dose level, at least 2 patients with 8-week follow-up will be required,
 - In case of important accrual rate, to maintain operating characteristics of TITE-CRM design and patient safety, the Sponsors might decide to suspend the inclusions.
 - The prior distribution of the dose-toxicity model will be chosen to control the expected number of toxicities in the trial under a variety of scenarios about the true relationship between dose and toxicity.
 - In the TITE-CRM paradigm, patients who have been enrolled in the trial but have not experienced DLT are included in the probability calculation with a weight equal to the proportion of the 13.5-week DLT observation period they have completed; patients who experience toxicity or completed the observation period without toxicity are assigned full weight.

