 - Stopping rule: inclusions will stop in the dose escalation trial after 24 eligible and assessable patients enrolled.
- For the dose escalation part, a DLT validation committee will be consulted before the first escalation to a new dose level (see section 12.1.2).
- Conclusions of the steering committee for the MTD definition will be submitted to an independent committee (IDMC) before opening the expansion cohort.

3.5.EXPANSION COHORT

- Once the MTD and the RP2D have been defined based on the dose escalation study, the expansion cohort will be opened. All patients will be treated at the RP2D of Olaparib (as defined in the escalation trial) given in association with concomitant radiotherapy at a dose that depends on tumor status:
 - Resectable tumor or potentially resectable tumor after study treatment: up to 50 Gy
 - Unresectable tumor: up to 59.4 Gy.
- Following the expansion cohort, the **RP2D for Olaparib** may be refined by the steering committee based on the MTD and RP2D (as defined at the end of the dose escalation trial), as well as additional safety data including safety data from the expansion cohort, PK and PD data. Data from all patients (escalation + expansion) will be used to refine the RP2D.

3.6.PATIENT'S REPLACEMENT

See section 10.2

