11.2.6. Intensity criterion

It is important to distinguish between serious and severe AEs. Severity is a measure of intensity whereas seriousness is defined by the criteria in Section 11.2.2. An AE of severe intensity need not necessarily be considered serious. For example, nausea that persists for several hours may be considered severe nausea, but not a SAE. On the other hand, a stroke that results in only a limited degree of disability may be considered a mild stroke but would be a SAE.

The CTEP Active Version of the NCI Common Terminology Criteria for Adverse Event (CTCAE) will be utilized for AE reporting.

The intensity of adverse events not listed in this classification will be assessed using the following descriptors:

Mild (grade 1): does not affect the patient's usual daily activities,

Moderate (grade 2): disturbs the patient's usual daily activities,

Severe (grade 3): prevents the patient's usual daily activities,

Very severe (grade 4): requires critical care/life-threatening,

Death (grade 5).

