11.3. SERIOUS ADVERSE EVENT AND NEW INFORMATION NOTIFICATION (RESPONSIBILITY OF THE INVESTIGATOR)

Serious adverse events will be reported by the investigator in the patient's CRF and will be followed up until complete resolution.

The investigator will notify the Vigilance Unit without delay about any serious adverse events or new events occurring:

- From the date of the informed consent is signed,
- During the whole patient treatment period as defined by the research,
- Until 30 days after the last dose of Olaparib and/or 6 weeks after the last dose of radiotherapy,
- Beyond this period of time, only those SAEs suspected to be related to the study treatment or the research (diagnostic procedures, examinations carried out during the research, surgery ...) will be collected without any limitation in terms of deadline. Nonetheless, the Sponsor will evaluate any safety information related to the clinical trial that is spontaneously reported by an Investigator beyond the time frame specified in the protocol.

Type of Event	Reporting procedure	Deadline for reporting to the sponsor
SAE	SAE Notification form + written report form if necessary	To be reported immediately to the sponsor
New information	Written report form	To be reported immediately to the sponsor
Pregnancy	Pregnancy Notification form + Written report form if necessary	As soon as pregnancy is confirmed

The investigator must complete the "Serious Adverse Event Notification Form" (Appendix 4) immediately, in English, and assess the relationship with the study treatment. The form must then be dated, signed and sent by fax to the following address without delay to:

CELLULE DE VIGILANCE (VIGILANCE UNIT) – Institut Bergonié [contact] Contact : Promotion Tél : [name] – Mail : [contact] [name] (pharmacien) Tél : [name] – Mail : [contact]

--

For each event, the investigator will record:

- A description of the event that is as clearly as possible, using medical terminology,
- The date AE met criteria for serious AE,
- The seriousness criteria,
- The date of hospitalization and the date of discharge,
- The probable cause of death and the date of death if appropriate,
- The date the event started and ended,
- The patient's relevant medical history,
- The steps taken and whether or not corrective treatment was required, whether or not the investigational treatment was discontinued, etc.
- Concomitant medications / therapies

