11.7. NON SERIOUS ADVERSE EVENT

TYPE OF EVENT	REPORTING PROCEDURES	DEADLINE FOR REPORTING TO THE SPONSOR
Non-serious AE	Case report/record form	Does not need to be reported immediately

Non-serious adverse events will be reported by the investigator in the patient's CRF and will be followed up until complete resolution.

The following variables will be collected for each AE:

- AE (verbatim)
- The date when the AE started and stopped
- Minimum and maximum intensity
- Whether the AE is serious or not
- Outcome
- Investigator causality rating against the Investigational Product (yes or no) radiotherapy (yes/no)
- Action taken with regard to investigational product/comparator/combination agent
- Treatments given to treat AE

If an adverse event becomes serious, it should be reported and followed-up as mentioned in the previous reporting procedures.

If the investigator would like to decrease trial treatment dose or temporarily stop study management without respecting protocol procedures, he/she should have previously discussed with the coordinator. However, symptomatic treatment can be prescribed to manage the adverse event.

Any definitive interruption of the procedure has to be immediately notified to the sponsor. The patient remains in the study and is followed-up according to the procedures described in the protocol.

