  - Interruption of radiotherapy for seven consecutive days or longer,
  - Interruption of Olaparib for 14 days or longer, whether this interruption happens on consecutive days or not.

A **DLT validation committee** will be consulted at each DLT notification for validation of the DLT status (see section 12.1.2).

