## 3.2 ENDPOINT ANALYSIS

### 3.2.1 PRIMARY ENDPOINT

#### 3.2.1.1 DOSE ESCALATION PART

- Toxicity graded using the common toxicity criteria from the NCI v4.03.
- Incidence rate of DLT at each dose level during treatment period up to six weeks after end of radiotherapy.

Criteria	eFORM variable	Control
Toxicity	EXA_RAD TOXI_RA EXA_ON TOXI_ON AEV4 AEVENT, AEECI (clinically interesting), DT_EIC, SOC, AESAE DT_SAE , DT_AE, DTENDAE (date of the end or death), INIT_INT, MAX_INT	
Check if the following variables are completed :
 
TOXI_RA TOXI_ON AEVENT AEECI DT_EIC SOC AESAE DT_SAE , DT_AE DTENDAE INIT_INT, MAX_INT
 
Data will be gathered in tables summarizing toxicities and side effects for each dose level and cycle.

Incidence rate of DLT	EXA_RAD DLT_RA EXA_ON DLT_ON DS_TOX DS_C10L (dose Olaparib) DT_TOX (Date tox)	
Check if the following variables are completed :
 
DLT_RA DLT_ON DS_C10L DT_TOX

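### A non-serious DLT has no reporting deadline, so a TITE-CRM allocation at a level already open can count a patient with a DLT as DLT-free; protocol and SAP also disagree on when DLTs are validated.

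*Protocol*

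**What the plan says.** **Allocation (Protocol 3.4.2).** Until the first DLT, patients enter in 3+3 cohorts. After it, each time a patient is ready to enrol, "the probability of DLT is estimated for each dose level, based on the trial experience up to that time" and on the prior. A patient with no DLT counts as DLT-free, weighted by the share of the 13.5-week window completed; a patient with a DLT has full weight. The assigned dose is the one whose estimate is nearest to 33% without exceeding it.

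**Registration (Protocol 6.2).** The coordinator assigns the dose level. The listed steps include no check of the DLT status of patients already on treatment.

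**Reporting.** For a serious event the deadline in Protocol 11.3 is "To be reported immediately to the sponsor". For a non-serious one, 11.7 says "Does not need to be reported immediately". Section 11.2.6 adds: "An AE of severe intensity need not necessarily be considered serious". Section 11.2.2 makes grade 4 laboratory results serious by rule, but not grade 3. Under 11.8.2, worsening of a protocol-mandated laboratory value becomes an adverse event only if it is serious or is the reason for stopping the product.

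**DLT definition (Protocol 3.3).** Several criteria need not involve a serious event: grade 3 non-haematological toxicity, a grade 3 laboratory abnormality lasting more than 5 days, and toxicity-related interruption of radiotherapy (7 consecutive days) or olaparib (14 days in total).

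**Validation.** Protocol 12.1.2: "the DLT validation committee will be consulted before the first escalation to a new dose level". SAP 1.1: the committee "will be consulted at each DLT notification for validation of the DLT status". For DLT incidence, SAP 3.2.1.1 lists the DLT flags from the radiotherapist and oncologist examination forms, with dose and date variables. The control there is "Check if the following variables are completed". No variable holds the committee's decision.

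**The concern.** TITE-CRM depends on current DLT data more than a design that waits for each cohort to finish. A patient whose DLT has happened but has not reached the sponsor is not simply missing from the model. That patient enters as partial evidence of safety, and the weight grows with follow-up. The next patient may then receive a dose that the trial's own 33% rule would exclude if the data were complete. If the late report concerns the first DLT of the trial, the switch from 3+3 to TITE-CRM is also delayed.

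The exposure is mainly at levels already open. A first move to a new level brings in the committee and the minimum follow-up rule. A further patient at an open level, or a return to a lower one, brings in neither.

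The validation conflict is a separate matter. The two documents give different triggers, and the SAP has nowhere to record the result, so the DLT rate, which is the primary endpoint, has no stated source of adjudicated status.

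**Working it through.** **1. The plan's own figures.** Window: 1 week of olaparib + 6.5 weeks of radiotherapy + 6 weeks = 13.5 weeks. By calendar, 33 fractions from D8 at five per week end on D52, and D52 + 42 days = D94, or 13.4 weeks. Sample size: 6 x 4 = 24 assessable; 26 + 15 = 41 in all. These reproduce.

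**2. Can a late report change the assignment at an open level?**

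From the documents: power model with a normal prior (Protocol 10.3), target 33%, closest but not above, weight = time completed / 13.5 weeks (3.4.2). Neither document gives the skeleton or the prior variance, so both are assumed.

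Model: p(level) = s^exp(a), a ~ N(0, 1.34). A patient with a DLT contributes p to the likelihood; a patient without one contributes 1 - w x p. Estimates are posterior means.

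Scenario: 3 patients DLT-free at level 1 and 3 at level 2, all fully observed. Two patients at level 3: one with a known DLT, one with an unreported DLT at w = 0.6 (0.6 x 13.5 = 8.1 weeks). Missed: the last patient contributes 1 - 0.6p. Counted: that patient contributes p.

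| Assumed skeleton | Level 3, missed | Level 4, missed | Level 3, counted |
|---|---|---|---|
| .05 .12 .22 .33 | 0.238 | 0.337 | 0.341 |
| .10 .20 .33 .45 | 0.260 | 0.365 | 0.362 |
| .12 .22 .33 .44 | 0.250 | 0.346 | 0.352 |
| .02 .08 .18 .33 | 0.244 | 0.384 | 0.348 |
| .15 .25 .33 .45 | 0.236 | 0.340 | 0.338 |
| .05 .10 .20 .30 | 0.233 | 0.324 | 0.335 |
| .08 .16 .25 .35 | 0.233 | 0.320 | 0.335 |

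In the first five rows, with the DLT missed, level 4 exceeds 33% and level 3 does not. The model assigns level 3, which is already open, so the protocol requires no committee step. With the DLT counted, level 3 exceeds 33%. In the last two rows the direction is the same, but the missed-DLT model points to level 4, where the committee step applies.

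A wider grid used four skeletons (rows 1, 2, 4 and 5), 2 to 5 patients at level 3 with w of 0.4 to 0.8, and 2 to 4 patients at level 2 with w = 0.6. One missed DLT changed the assigned level in 40 of 48 + 12 of 12 = 52 of 60 settings. In 19 + 11 = 30 of these, the uncorrected model assigned a level already open.

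The margins above 33% are thin. With prior variance 0.5 in the scenario above, the counted level 3 estimate runs from 0.31 to 0.35 and exceeds 33% under three of the seven skeletons. With variance 2 it does so under all seven.

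These are outputs of an assumed model, not dose recommendations.

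**3. How likely is an enrolment during a delay?** Planned accrual (Protocol 5.1): 41/56 = 0.73 per month, or 0.73 x 12/52 = 0.169 per week, about 2.3 patients per 13.5-week window. With Poisson arrivals, P(at least one) = 1 - exp(-0.169 x delay in weeks):

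- 1 week: 16%
- 2 weeks: 29%
- 4 weeks: 49%

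For assumed accrual of 0.5 to 2 per month, the range is 21 to 60% at 2 weeks and 37 to 84% at 4 weeks. The delays are assumptions, and the probabilities are conditional on a DLT staying unreported that long.

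**The case against.** The case that this is only a wording matter has real content.

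- **Other routes to the sponsor.** A definitive interruption must be notified at once (11.7). Toxicities that would modify the dose should be discussed with the sponsor (7.1.6.1). Section 7.2.5 labels in-field grade 3 toxicity before 30 Gy, or persisting beyond 4 weeks, as a DLT that stops olaparib; if that stop is definitive, it is notifiable. Entered eCRF data are transferred and monitored in real time (12.2.1). Radiotherapist visits are weekly during irradiation. These shorten likely delays, but none is a DLT deadline, a data-entry deadline or a check before allocation.
- **The registration SOP.** Doses are assigned under a sponsor SOP that is not among these documents. It may contain a status check, so one can say only that the protocol lists none.
- **Modest exposure.** For a one-week delay the chance of an enrolment is 16%, the assignment did not change in 8 of 60 grid settings, and the sponsor may suspend inclusions. This stands, and it limits the severity.

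A reader might also infer more than the documents support:

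- *That a missed DLT opens the way to level 4 unchecked.* A first escalation requires the committee and, at level 3, two patients with 8 weeks of follow-up.
- *That missing validation makes a DLT count as DLT-free.* It does not. A reported but unvalidated DLT still counts, and moves the model towards lower doses. The harm in allocation comes from late reporting.
- *That unvalidated DLTs settle the MTD unreviewed.* The discretionary DLT category requires discussion with the sponsor (3.3). The steering committee's conclusions go to the IDMC before expansion (3.3, 12.1.3).
- *That the SAP's trigger is a working safeguard.* Its synopsis still describes a 3+3 design, so it shows a conflict between documents, and it sets no notification deadline either.

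**Conclusion.** The point holds as a procedural gap that should be fixed; it does not invalidate the design. Followed as written, the protocol allows a non-serious DLT to be unknown when the next dose is assigned. A non-serious grade 3 laboratory DLT may not be recorded as an adverse event at all.

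In the illustration, one missed DLT lowers the level 3 estimate by about 0.10, enough to cross the 33% limit under all seven skeletons at prior variance 1.34, and to do so without a committee step under five. That size rests on the assumed skeletons, variance and follow-up weight; a tighter prior weakens it. The frequency rests on assumed reporting delays. The absence of a DLT deadline and of a listed status check, and the conflict over the validation trigger, rest on the text alone.

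**What to change.** 1. **Protocol 11.3, 11.7 and 11.8.2:** make every suspected DLT, serious or not and including laboratory DLTs, immediately reportable to the sponsor by the existing SAE route.
2. **Protocol 6.2 and 3.4.2:** require the coordinator to confirm and document the DLT status of all patients still in the 13.5-week window before each dose assignment.
3. **Protocol 3.3, 3.4.2 and 12.1.2, and SAP 1.1:** state one committee trigger in both documents. Consultation at each DLT notification, as in the SAP, would also cover levels already open.
4. **SAP 2.1.1 and 3.2.1.1:** add a committee-validated DLT field, use it for the DLT rate and the model, and list disagreements with the examination-form flags. Say how a DLT awaiting validation enters the model.

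The cost is wording in two documents and one database field. The three-person committee and the reporting route already exist. The downside is a few more short consultations and a brief delay to some allocations.

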12.1.3. Independent Data Monitoring Committee

- An independent Data Monitoring Committee (IDMC) will be created at the request of the relevant Authority, the sponsor or the Steering Committee. The IDMC plays an advisory role for the Sponsor, who has the final decision regarding the implementation of recommendations put forward by the IDMC.
- Conclusions of the steering committee for the MTD and RP2D definitions based on the dose escalation trial will be submitted to the IDMC before opening the expansion cohort. If necessary, a second IDMC may be set up at the end of the expansion cohort.
- Implementation of the IDMC committee will be performed according to the internal procedures at Institut bergonié.

Composition of the IDMC

- This Committee must comprise at least one qualified oncologist, one radiotherapist, one pharmacologist and one statistician:
 - Qualified oncologist ([name])
 - Radiotherapist ([name])
 - Pharmacologist ([name] [name])
 - Statistician ([name])

All of whom will have experience in the monitoring and analysis of clinical trials. One of these members will be appointed as the Trial Rapporteur.

- Each of these members must be unconnected with the trial and cannot, therefore, be one of the trial investigators.

- These members are appointed by the Sponsor in consultation with the trial co-ordinator and the Steering Committee.

Responsibilities of the IDMC

The IDMC is responsible for the following:

- Analyzing preliminary efficacy and safety data, specifically the statistical report presenting results for the dose escalation part will be presented to the IDMC experts;
- Making recommendations on the continuation, early discontinuation (in the case of toxicity or lack of efficacy) or publication of the trial results,
- Drafting the minutes after each meeting and monitoring their confidentiality.

Any recommendation from the IDMC that can be made public will be announced by the Sponsor and not by the Steering Committee. The Sponsor is responsible for sending IDMC recommendations to the regulatory authorities [ANSM (French Agency for the Safety of Health Care Products) and EMEA (European Medicines Evaluation Agency)].

12.2. QUALITY ASSURANCE

12.2.1. Data collection

The data will be collected on an electronic case report form and directly input via the Internet. Only the investigators and the Investigator's Clinical Research Assistants (CRAs) appointed by the sponsor and duly authorized by the sponsor will be authorized to enter the data.

Data will be handled by an online trial management software on the Internet (Macro v4, Infermed Company); it will be transferred and monitored remotely in real time.

The study CRA and/or any other person appointed by the sponsor will be available to assist the investigators in carrying out the study and to ensure that the trial is carried out in accordance with the protocol.

The study CRA will contact the investigators regarding the study implementation visit.

All of the necessary data will be collected on an electronic case report form provided by the sponsor. The generic names of the concomitant medication will be given in French.

Corrections made to the original data must be justified. These corrections will be automatically dated and signed by the authorized member of staff via the personalized password allocated at the start of the study.

The case report form will be validated by the investigator or the CRA at the authorized center whenever data is entered.

Laboratory data exceeding normal limit values will be commented upon if they are considered clinically significant. Data other than that requested within the scope of the protocol can be collected as additional data; their interest will be specified.

12.2.2. Monitoring

In order to guarantee the authenticity and credibility of the data in accordance with the principles of GCP (Good Clinical Practice) dated 24 November 2006, the sponsor shall implement a quality assurance system comprising:

- the management and monitoring of the trial in accordance with the procedures stipulated by the Institut Bergonié,
- the quality control of the research site data by the CRA whose role is to:
 - check compliance with the protocol, GCP and current legislation and regulations,
 - check the consent and eligibility of each patient taking part in the trial,
 - check the consistency and coherence of case report form data against the source documents.
 - check that each serious adverse event is reported,
 - monitor the traceability of the study medication (dispensation, storage and drug accountability),
 - check, where applicable, that the persons likely to take part in the trial are not already participating in another trial that could prevent them from being included in the clinical

trial proposed. The CRA shall also ensure that the patients have not participated in a trial for which an exclusion period currently applies.

- The possible audit of study centers
- The centralized review of certain protocol criteria.

The check procedures will include:

- Study progression,
- Protocol compliance,
- The updating of information on the Internet site.

The checking of data by comparing the information on the electronic case report form and the original clinical or laboratory data is one of the monitoring procedures.

The following will be checked, in particular, for each patient (100% level): patient identification, informed consent (procedure and signature), selection criteria, therapeutic procedure, adverse events, principal response variables. The personal data relating to each patient shall remain confidential. On the electronic case report form or any other form dispatched, the patients will be identified solely by their initials (1/name – 1/surname) and an inclusion number. However, the investigators must keep a list identifying the patients in their folders.

The CRAs responsible for the quality control of this clinical trial are duly appointed by the sponsor for this particular purpose and must have access, with the consent of those involved, to individual trial participant data required strictly in accordance with this control procedure. The CRAs are subject to professional secrecy under the conditions defined by Articles 226-13 and 226-14 of the French penal code. The traceability of monitoring visits is guaranteed by a written monitoring report.

The investigators shall undertake to give CRAs direct access to the medical records of each patient in order to allow the CRAs to ensure optimal quality control of the trial. The same applies to health authority representatives.

